The intervention will include use of a PE audit and feedback tool implemented by district personnel within the 5 intervention schools. The current PE Works audit and feedback tool consists of 9 binary (yes/no) PE quantity and quality indicators, including whether or not: 1) The school employs credentialed PE teachers and whether or not they teach an appropriate number of students at a time; 2) At least 200 minutes of PE and whether or not they teach an appropriate number of students at a time; 2) At least 200 minutes of PE are scheduled every 10 days, per CA education law; 3) PE class content meets instructional standards; 4) PE teachers participate in appropriate staff development and training; 5) School communicates with families about PE; 6) The school community is educated about physical activity and wellness opportunities; 7) The school's education plan includes wellness goals; 8) There is designated PE space where students can move safely; 9) The school fosters a PE culture that is inclusive of all students. This is the type of data that will be obtained/recorded by district personnel during onsite school observations and conversations with the school principal. District-level PE employees complete an onsite audit of the 9 indicators (through visual assessment and discussion with school administrators and teachers). No information about individuals will be obtained, collected, or recorded during these observations and discussions.

Once completed, data are entered into a database and a visually-pleasing 2-page report is produced for each school that: 1) describes all 9 components that were assessed; 2) highlights components where the school is succeeding; and 3) details components that need improvement, providing suggestions on how to do so. No information about individuals be entered into the database in order to generate the report. Data from the Audit and Feedback Report will be used as part of our research. We will use the 9 binary (yes/no) indicators from the report in our

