REDACTED DISTRICT personnel will be trained to implement the PE audit and feedback tool in the fall of pilot year 1 (PY1) and will collect audit data in the spring. REDACTED DISTRICT will give feedback to school principals during one-on-one meetings in the fall of PY2. The intervention will take place over 2 years (PY2 and PY3). At the start of PY1-PY3, researchers will obtain school-level PE master schedules, which contain PE times for all classes in the school. Administrators at participating schools will either provide study team contact information to prospective 2nd and 5th grade teacher participants or will forward a recruitment email that the research team has written onto prospective participants so that prospective participants may make the first point of contact with our team if they are interested in participating. Our team will not be provided with names or contact information of prospective participants in order to recruit prospective participants. All recruitment materials and consent forms will emphasize the voluntary nature of participation in the research and that participants are free to skip/not answer any question that they do not wish to answer and are free to stop participating in the research at anytime. Once consented to participate, researchers will collect 2nd and 5th grade teachers' individual classroom PE schedules (we know PE operates differently in lower (Kindergarten – 2nd) and upper (3rd – 5th) elementary grades, which is why these two grades have been chosen.

During the fall and spring of PY1-PY3 we will collect objective data on PE class length and proportion of class spent in moderate to vigorous physical activity using the validated System for Observing Fitness Instruction Time (SOFIT) tool, observing 3 PE classes of 2 randomly selected 2nd and 5th grade teachers (n=4 teachers) and the PE teacher (if there is one) at each school on random days, per semester. Random day selection for observation days allows verification of self-reported PE minutes. SOFIT data will be collected by members of the research team who have been trained in the SOFIT protocol (and who have been CITI certified) and who have been fingerprinted and background checked and approved to visit REDACTED DISTRICT schools.

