The observer will arrive 15 minutes prior to the scheduled start of the PE class to situate him/herself. During observations investigators will have no interactions with teachers or students. Once the class has arrived at the PE area (i.e. gym or blacktop), the observer will randomly select four target students to observe during the lesson (2 girls and 2 boys). No individually identifiable information will be collected on students being observed. The observer will observe Student One for 4 minutes and then rotate to focus on the four students for four minutes each until the lesson ends. A pacing MP3 played through headphones will prompt the observer to collect data every 20 seconds on 1) the activity level of the student being observed (ranging from 1 (sedentary) to 5 (very active)) and 2) what type of activity the whole class is engaged in (game play, fitness, skill acquisition, knowledge acquisition, management, or other). The observer will begin the observation period when the teacher and 51% of the class has reached the instructional station and continue until half the class has departed from the area. The observer will also collect information at the class level, including on the length (in minutes) or the PE class, weather conditions if the class took place outside, class size (and number of boys and girls in the class), and whether the teacher was administering the state FitnessGram test during class. The only identifiable information that will be collected will be the teacher name (this enables the observer to make sure he/she is observing the correct PE class), the teacher type (2nd grade, 5th grade, or PE), and the teacher's sex (M/F).

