Teacher and/or student participation during the observation portion of Phase 2 requires no extra time commitment of participants outside of their normal PE class. Members of the research team will not be asking the schools/district to implement curriculum changes. Instead, we will be evaluating whether or not the tool provided feedback to the schools in a manner that allowed the schools to make the necessary changes in order to comply with state law. We will assess adoption, implementation, and maintenance of the PE audit and feedback tool through interviews with: district-level personnel involved in implementing the PE audit and feedback tool; principals in the 5 intervention schools; and all 2nd grade, 5th grade, and PE teachers observed in intervention schools. We will also conduct interviews with principals and teachers observed in the 5 control schools. These interviews will take place in PY2 and PY3 and will last approximately 20-30 minutes each. If a teacher or administrator participates in the study during both years, he/she will be interviewed twice (once in PY1 and once in PY2, after SOFIT observations are conducted in the spring). A semi-structured interview guide will enable the collection of data to assess RE-AIM components, including questions about: who teaches PE; priority for PE; the use of the PE audit and feedback tool; barriers encountered; successes and struggles with providing and sustaining mandated PE minutes; and plans for continuing to implement the PE audit and feedback tool and provide mandated minutes.

Statistical Analysis Plan

School-level demographic data will be downloaded from the California Department of Education's Data Quest website. Differences in school-level characteristics between all district elementary schools and study schools, as well as between intervention and control schools, will be determined using unpaired t-tests. Linear mixed effects models with random effects for school and grade will be used to determine 1) within-group changes and 2) difference in change between intervention and control schools in: scheduled minutes of physical education/week;

estimated minutes of physical education/week; and the proportion of observed lesson time in MVPA. All analyses will be performed using Stata/ SE (16.1).

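### The mixed model has no teacher or school-by-year term, so the standard error for the difference in change between 5 and 5 randomised schools is likely to be too small

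*Combined protocol and SAP*

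**What the plan says.** The model is stated once, in the Statistical Analysis Plan: "Linear mixed effects models with random effects for school and grade will be used". It serves both the changes within each arm and the contrast between arms. The outcomes are scheduled PE minutes per week, "estimated minutes of physical education/week; and the proportion of observed lesson time in MVPA". The plan names no other random term, does not say whether grade is crossed with school or nested in it, and gives no degrees-of-freedom method.

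The Study Protocol gives the data structure. Ten schools are randomised, 5 to each arm. Lessons are observed in fall and spring of three pilot years, "observing 3 PE classes of 2 randomly selected 2nd and 5th grade teachers (n=4 teachers"). A fifth teacher may be added to these four: "and the PE teacher (if there is one) at each school". The two grades were picked because PE runs differently in lower and upper elementary grades, "which is why these two grades have been chosen". The observer records the teacher's name and "the teacher type (2nd grade, 5th grade, or PE").

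**The concern.** Treatment is assigned to schools, so a change over time in the intervention arm should be compared with how much schools drift from year to year without intervention. A random intercept for school removes stable differences between schools. It does not represent a school having a good or bad PE year (a new timetable, a new principal, a lost gym), nor the resemblance among lessons given by one teacher. A random intercept for grade, crossed or nested, is also constant over time and does not fill the gap. Both sources are then treated as independent lesson noise, and many lessons stand in for few schools.

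At stake are the within-group changes and the between-arm contrast for a tool that the protocol hopes will prove cost-effective and scalable. Chance drift in a few schools could be reported as an effect.

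Two smaller gaps lie in the same sentence of the plan. Grade has two purposely chosen levels but is treated as random. PE-teacher lessons have no stated coding.

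**Working it through.** The plan reports no power, variance or lesson total, so there is no figure of its own to reproduce.

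**Inputs from the Study Protocol.** 10 schools; 4 grade teachers × 3 lessons = 12 lessons per school-semester; 2 semesters × 12 = 24 lessons per school-year.

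**Assumptions.** Within-school variance is set to 1. Teacher share τ is 0.10 or 0.20; school-year share ω is 0.02 or 0.05; the rest is lesson noise. PE-teacher lessons are left out of this calculation.

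**Step 1: variance ratio.** Take one school's change from PY1 (24 lessons) to PY2-PY3 (48 lessons).

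- With a school intercept only, the model uses about 1/24 + 1/48 = 1/16.
- If teachers are redrawn each semester, there are 8 teacher draws in PY1 and 16 in PY2-PY3. The true variance is (1 − τ − ω)/16 + τ(1/8 + 1/16) + ω(1 + 1/2).
- Dividing by 1/16 gives 1 − τ − ω + 3τ + 24ω = **1 + 2τ + 23ω**.
- If teachers are redrawn each year, τ(1/4 + 1/8) replaces the teacher term, and the ratio is **1 + 5τ + 23ω**.

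These are the usual design effects: 3 − 1 = 2 or 6 − 1 = 5 for teacher, and 24 − 1 = 23 for school-year.

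**Step 2: false-positive rate** = 2 × [1 − Φ(1.96/√ratio)].

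| τ | ω | Ratio, redrawn each semester | Rate | Ratio, redrawn each year | Rate |
|---|---|---|---|---|---|
| 0 | 0 | 1.00 | 5.0% | 1.00 | 5.0% |
| 0.10 | 0 | 1.20 | 7.4% | 1.50 | 11.0% |
| 0.20 | 0 | 1.40 | 9.8% | 2.00 | 16.6% |
| 0 | 0.02 | 1.46 | 10.5% | 1.46 | 10.5% |
| 0 | 0.05 | 2.15 | 18.1% | 2.15 | 18.1% |
| 0.20 | 0.05 | 2.55 | 22.0% | 3.15 | 26.9% |

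**Step 3: simulation under no effect.** With school intercepts only and teachers redrawn each semester, the rates were 5.2% (neither source), 7.7% and 10.2% (teacher 10%, 20%), 11.7% and 19.7% (school-year 2%, 5%) and 23.7% (teacher 20% with school-year 5%). A second simulation gave about 8-18% for teacher alone, 11-20% for school-year alone and 23-29% for both. A t-test on the 10 school changes gave 4.6-5.4%. The formula and the simulations agree closely.

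**Step 4: grade.** Crossed with school, two grades leave 1 df, and the 95% chi-square interval for the grade variance runs from 1/5.02 = 0.20 to 1/0.00098 ≈ 1,018 times the estimate. Nested in school, there are 20 school-by-grade units and 10 df, and the interval is 0.49 to 3.1 times. In 60 balanced simulated datasets the arm-by-time estimate was identical with grade fixed, crossed or nested (mean standard errors 0.188, 0.188 and 0.182).

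**Step 5: PE-teacher lessons.** Where a school has a PE teacher, 3/(12 + 3) = 20% of observed lessons. Over the study this is 180/900 = 20% if all schools have one, 90/810 = 11% if half do, and 0% if none do.

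**The case against.** The best reply is that the variance shares are assumed and that the protocol does not say whether teachers are redrawn. If the same teachers were followed throughout, constant teacher effects would cancel from the change. The ratio becomes 1 − τ + 23ω: 0.90 or 0.80 with no school-year variation, which gives rates of 3.9% or 2.8%, below nominal. This stands, and the teacher part of the concern depends on turnover. Full continuity over three years is not promised, however: the protocol treats a teacher's taking part in both interview years as only a possibility. The school-year part does not depend on it. With every teacher retained, τ = 0.20 and ω = 0.02 give 1.26 (8.1%), and τ = 0.10 and ω = 0.05 give 2.05 (17.1%).

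It is also fair to say that this is a 10-school pilot, and that the lesson counts apply to outcomes built from observed lessons. Scheduled minutes can come from master schedules covering all classes. School-by-year variation matters there too if several classes per school enter the model, but its size is not worked out here.

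A reader might infer more from the grade term: that its variance cannot be estimated, or that PE-teacher lessons cannot enter the model. The documents do not support either. The plan does not say whether grade is crossed or nested; nested, the variance is estimable, and crossed, it is estimable but nearly uninformative. The 0.20 to 1,018-fold interval belongs to the crossed reading alone. PE can be a third level, and the list of recorded class items need not be complete, so the grade of a PE-teacher's class may be recoverable.

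**Conclusion.** The concern holds for the missing variance terms. Followed as written, the model is likely to give standard errors for the within-group changes and the difference in change that are too small. With teacher shares of 10-20%, school-year shares of 2-5% and teachers who change between semesters or years, the false-positive rate is about 8% to 29% against a nominal 5%. Those shares are assumptions; with no school-year variation and the same teachers throughout, there would be no inflation.

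The grade and PE-teacher points are unclear specification. Treating grade as fixed or random did not move the arm contrast in balanced data. A reader might also infer bias from dropped PE-teacher lessons, since the first audit indicator includes whether "The school employs credentialed PE teachers". That would require the tool to change staffing, the analyst to drop the lessons, and the loss to differ by arm. The documents show none of these, although they leave the handling of these lessons open until data are in hand.

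**What to change.** Replace the model sentence in the Statistical Analysis Plan with a full specification:

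- fixed effects for arm, time and their interaction, with the years compared stated;
- random intercepts for school, for teacher within school and for school-by-year;
- a small-sample degrees-of-freedom correction such as Kenward-Roger. The alternative is a comparison of the 10 school-level changes;
- grade as a fixed factor, because the two levels were chosen on purpose;
- PE-teacher lessons kept as their own category, so that teacher type has three levels.

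Teacher type may itself change after the intervention, and adjusting for it could then remove part of the effect. Report the contrast with and without that adjustment. State also whether teachers are redrawn or followed.

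No new data are needed, because teacher name and type are already recorded. The cost is precision. Under the ratios of 1.20 to 3.15 above, standard errors rise by factors of √1.20 = 1.10 to √3.15 = 1.77. In the comparison of 10 school changes, the t critical value on 8 df is 2.306 instead of 1.96, a further factor of 1.18. The wider intervals are what 10 schools can support.
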